2.0 Study Summary

2.1 **Title:** Esmolol to Control Adrenergic Storm in Septic Shock (ECASSS) – ROLL-IN

2.2 **Objective:** To evaluate the adequacy and efficiency of study protocols for the main ECASSS study.

2.4 **Study design:** Prospective, single arm, feasibility (“roll-in”) study of esmolol infusion in septic shock.

1. **Inclusions.** We will include patients admitted to the ICU for sepsis who are within 48 hours of septic shock and ICU admission and are simultaneously tachycardic (heart rate >90/min) **and** on vasopressors for > 60 min. Patients must meet criteria at the time of enrollment.
2. **Final safety check.** After enrollment and before esmolol infusion, ScvO₂, transthoracic echocardiogram, evaluation of fluid responsiveness, and review of telemetry/EKGs will occur to assure that no exclusion criteria are present.
 - a. If no exclusion criteria are present, patients will start esmolol infusion
 - b. If patient is still fluid responsive but otherwise has no exclusions, fluid will be administered by explicit protocol until no longer fluid responsive, and then the patient will receive esmolol infusion. If tachycardia has resolved as a result of volume expansion, esmolol infusion will not occur until tachycardia and vasopressor administration co-occur. After esmolol infusion, volume expansion will be managed as part of the esmolol titration protocol.
 - c. Patients who fail the final safety check will NOT start esmolol infusion but will be followed for non-interventional aims (e.g., serial TTEs, vascular biomarkers) to understand better the natural history of cardiogenic shock superimposed on septic shock.
3. **Esmolol infusion**
 - a. Esmolol infusion, started without bolus, with slow upward titration to a maximum infusion rate is protocolized (see protocol in Appendix 1), with a target heart rate of 80-90/min.
 - b. Esmolol infusion will be stopped in the event that cardiogenic shock, excessive bradycardia, grade 2 or grade 3 heart block, or hypotension, or bronchospasm occur, as per protocol.
4. **Other care**
 - a. ICU patients are managed according to current Surviving Sepsis campaign guidelines as per usual practice.
 - b. Vasopressor infusion titrations according to protocol are recommended, while clinicians retain the ability to titrate as they feel clinically indicated. Norepinephrine should be the primary vasopressor; at 0.25 mcg/kg/min of norepinephrine, a second vasopressor agent (preferentially, vasopressin 0.03 units/min or epinephrine) may be added; at 0.5 mcg/kg/min, stress-dose steroids (hydrocortisone 150-200 mg IV daily or equivalent, in divided doses) may be added.

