5.2 Esmolol infusion

The esmolol infusion will be managed as per the protocol in APPENDIX 1. Esmolol will be stopped and cannot be restarted without explicit investigator approval for STOP events. Further needs for volume expansion will be assessed on the basis of VOLUME EXPANSION events. If the patient is taken to the operating room, esmolol

infusion will be stopped when the patient leaves the ICU for the OR and will only be resumed after reevaluation of cardiac index and adequacy of volume expansion, given the possibility of changes in volume status and degree of shock during surgery.

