8.2 Risk abatement strategies

8.2.1 Cardiogenic shock. As indicated above, patients with preexisting cardiogenic shock are excluded from enrollment, and after enrollment a formal evaluation to exclude cardiogenic shock will be performed before esmolol infusion. The esmolol titration protocol incorporates continuous monitoring of cardiac output using the non-invasive NICOM™ device, and in the rare situation that cardiogenic shock should ensue, esmolol titration will be discontinued and appropriate supportive measures will be instituted. Our use of a no-bolus, slow upward titration protocol for the esmolol infusion is specifically designed to avoid this potential complication.

8.2.2 Excessive bradycardia and/or hypotension. As indicated above, patients with preexisting conduction system disease are excluded from enrollment, and a formal evaluation to exclude conduction system disease will be performed before esmolol infusion. In the event that hypotension or excessive bradycardia should ensue during esmolol infusion, esmolol will be discontinued and appropriate supportive measures will

be instituted. Our use of a no-bolus, slow upward titration protocol for the esmolol infusion is specifically designed to avoid this potential complication.

8.2.3 Hypersensitivity reaction. This is extremely rare. Patients with known hypersensitivity to esmolol or vehicle are excluded from the study. Should this occur, esmolol infusion will be stopped and appropriate treatment measures will be instituted. The short half-life of esmolol avoids concerns about treatment of anaphylaxis in patients on β -blockers, should anaphylaxis occur.

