ECASSS ROLL-IN Study Drug Titration protocol

Fundamental rules for study drug titration:

The target heart rate is 85 bpm. Start study drug infusion at 20 mcg/kg/min, without bolus, if HR \geq 100 bpm. If HR >90 bpm and <100 bpm, start study drug infusion at 10 mcg/kg/min, without bolus. Increase by 20 mcg/kg/min every 20 minutes as long as HR > 90 bpm, to a maximum dose of 100 mcg/kg/min. If HR < 80 bpm and > 70 bpm, decrease infusion rate by 10 mcg/kg/min; if HR ≤ 70 bpm and > 60 bpm, decrease infusion rate by 20 mcg/kg/min. Stop study drug infusion whenever a STOP EVENT occurs. Study drug infusion is completed 3 hours after vasopressor infusions have stopped. The up-titrations can be smaller than stipulated if the clinician and/or investigator feels that a small up-titration is indicated. Up-titrations should not occur during a REASSESS VOLUME STATUS event.

Study drug should be preferentially infused centrally; where no port is available, study drug should **not be** infused into a small peripheral vein or via butterfly catheter.

STOP EVENTS:

1. If HR is ever ≤ 60 bpm, immediately stop infusion for 20 minutes, then restart at half the previous infusion rate, rounded to nearest 10 mcg/kg/min. Do not resume infusion until HR > 70 bpm.
2. If vasopressor dose increases by 0.2 mcg/kg/min norepinephrine (or equivalent) AND doubles within 60 min despite adequate volume expansion, STOP the study drug infusion. Alternatively, if the treating clinician believes that the shock is worsening significantly, STOP the study drug infusion. Do not resume without explicit approval of study physician.
3. If cardiogenic shock develops ($ScvO_2 \leq 60\%$ OR LV Ejection Fraction $\leq 25\%$ OR Cardiac Index ≤ 2.0 L/min/m²), STOP the study drug infusion. Do not resume without explicit approval of study physician.
4. If clinically apparent bronchospasm develops, STOP the study drug infusion. Do not resume.
5. If Grade 2 or Grade 3 heart block develops, immediately STOP the study drug infusion. Do not resume.

REASSESS VOLUME STATUS EVENTS:

When markers of potential preload deficit occur (urine output < 0.5 ml/kg/hr OR vasopressor dosage increase), immediately EVALUATE FOR VOLUME RESPONSIVENESS. A vasopressor dosage increase is defined as at least 0.05 mcg/kg/min absolute AND 20% relative increase in the norepinephrine (or equivalent) infusion.

Titrate vasopressors as per local practice to maintain MAP ≥ 65 mmHg. Norepinephrine is the preferred primary vasopressor.

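### The 100% STOP-compliance outcome in section 2.8 uses rules that differ from Appendix 1, and the restart rule in section 5.2 conflicts with STOP event 1

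*Combined protocol and SAP*

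**What the plan says.** Section 5.2 makes Appendix 1 the operating protocol: "The esmolol infusion will be managed as per the protocol in APPENDIX 1". Appendix 1 lists five numbered STOP events.

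**Compliance.** Section 2.8 item 3b treats STOP compliance as adequate only at 100%. Under that standard it lists three items: cardiac index averaged over a moving 30 minutes and below a threshold; norepinephrine rate averaged the same way and above a threshold; and the clinician's judgement that shock has become substantially worse. It gives no value for either threshold and does not say whether the list is complete.

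**Restart.** Section 5.2 states: "Esmolol will be stopped and cannot be restarted without explicit investigator approval for STOP events". For a heart rate of 60 bpm or below, Appendix 1 event 1 says to "immediately stop infusion for 20 minutes, then restart at half the previous infusion rate". Its only further condition is "Do not resume infusion until HR > 70 bpm". Events 2 and 3 each say "Do not resume without explicit approval of study physician". Events 4 and 5 do not allow the infusion to resume.

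**Hypotension.** Section 2.4 item 3b says esmolol is "stopped in the event that cardiogenic shock, excessive bradycardia, grade 2 or grade 3 heart block, or hypotension, or bronchospasm occur, as per protocol". Section 8.2.2 says: "In the event that hypotension or excessive bradycardia should ensue during esmolol infusion, esmolol will be discontinued". In Appendix 1, mean arterial pressure (MAP) appears only as the target for vasopressor titration.

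**The concern.** The roll-in exists to test whether the protocols are adequate for the main trial, and section 7.2 says its data will confirm compliance with them. STOP compliance is the outcome that bears most directly on safety. If the rule that is scored differs from the rule used at the bedside, a 100% result does not show that the Appendix 1 stops were made. A stop that Appendix 1 required but nobody made could leave the figure untouched.

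The restart texts raise a practical question about a beta-blocker after bradycardia. Staff who follow event 1 exactly as written breach 5.2. It is then unclear whether that restart counts as compliant.

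The hypotension wording is a smaller matter. Readers of 2.4 and 8.2.2 are told of a stop that the bedside list does not define in those terms.

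**Working it through.** **1. Appendix 1 set against section 2.8 item 3b and section 5.2**

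Event 2 contains two separate triggers and event 3 contains three, so five events give 1 + 2 + 3 + 1 + 1 = 8 triggers.

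| Event | Appendix 1 trigger | In 2.8 item 3b? | Restart under Appendix 1 |
|---|---|---|---|
| 1 | Heart rate ≤ 60 bpm | No | Half rate after 20 min, once heart rate > 70; no approval step |
| 2 | Norepinephrine-equivalent rise of 0.2 mcg/kg/min and doubling, within 60 min, despite adequate volume expansion | In another form: 30-min average rate, threshold unstated | Study physician approval |
| 2 | Clinician believes shock is significantly worse | Yes | Study physician approval |
| 3 | Cardiac index ≤ 2.0 L/min/m² | In another form: 30-min average | Study physician approval |
| 3 | ScvO₂ ≤ 60% | No | Study physician approval |
| 3 | LV ejection fraction ≤ 25% | No | Study physician approval |
| 4 | Bronchospasm | No | None |
| 5 | Grade 2 or 3 heart block | No | None |

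Three of eight triggers have a counterpart in 2.8, two of them in altered form, and five have none. By numbered event, the list touches two of five (events 2 and 3). No trigger is defined by hypotension or MAP.

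Section 5.2 conflicts with event 1, agrees with events 2 and 3, and is looser than events 4 and 5, which rule out any restart.

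**2. What the 30-minute average does to cardiac index**

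The only cardiac index figure in the documents' STOP rules is the 2.0 limit in Appendix 1. I assume that item 3b means the same limit. The starting and lower values below are assumptions, chosen to show the mechanism.

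After a step fall from s to d, the 30-minute average at t minutes (t ≤ 30) is s − (s − d) × t/30. It reaches 2.0 at t = 30 × (s − 2.0)/(s − d).

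- 2.5 to 1.5: 30 × 0.5/1.0 = 15.0 min
- 3.0 to 1.8: 30 × 1.0/1.2 = 25.0 min
- 4.0 to 1.9: 30 × 2.0/2.1 = 28.6 min

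In each case Appendix 1 is met at once. For a dip from 3.0 to 1.8 that lasts 20 minutes, the lowest average is 3.0 − 1.2 × 20/30 = 2.2. Appendix 1 requires a stop, but item 3b as written never registers the event.

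**3. Norepinephrine**

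Event 2's numeric limb depends on the starting rate b. The rate must reach the larger of b + 0.2 and 2b, within 60 minutes and despite adequate volume expansion. From 0.10 that is 0.30 mcg/kg/min; from 0.50 it is 1.00. No single fixed rate can reproduce this rule, and item 3b states no value in any case.

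**4. Does item 3a fill the gap for heart rate?**

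Only in part. It scores whether heart rate lies within 77 to 93 bpm at the hourly reading and at the start and end of the infusion, with over 80% as adequate. It does not score whether the infusion was stopped when heart rate fell to 60 or below.

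**The case against.** **The list in 2.8 may be illustrative.** Item 3b applies its standard to STOP events, a term that Appendix 1 defines, and does not call its list exhaustive. A reader might infer that the five unlisted triggers will definitely go unscored. The text does not establish that. It leaves open what is scored, and for an outcome with a 100% standard that is itself a defect. The objection also does not explain the different form of the two measured items.

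**The 30-minute window may be deliberate.** Secondary outcome 7 in section 2.8.2 counts a cardiac index of 2 or below only if it lasts more than 30 minutes on NICOM, so the window may be a considered way to handle that device's readings. That is plausible. It also shows that the protocol writes a duration where it wants one, and STOP event 3 has none.

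**Appendix 1 prevails on restart.** If Appendix 1 governs, the specific rule in event 1 could be read as overriding the general sentence in 5.2, and a team that seeks approval satisfies both texts. Both points are fair. But 5.2 states its approval rule immediately after naming Appendix 1 and makes no exception. Since events 2 and 3 spell out an approval step, its absence from event 1 looks intended.

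**Hypotension is covered.** A reader of 2.4 and 8.2.2 might infer that esmolol would continue through hypotension because no STOP event names it. The documents do not support that. Section 2.4 defers to the protocol, every patient is on vasopressors titrated to a MAP of at least 65 mmHg, and event 2 allows a stop for vasopressor escalation or on clinician judgement alone. Event 3 adds a stop for low output, with a titration protocol that "incorporates continuous monitoring of cardiac output using the non-invasive" NICOM device, and event 1 applies if heart rate falls to 60. A reader might also infer that a stop for hypotension would escape reporting. Section 10.1 separately collects serious events, non-serious events of related or uncertain relationship, and events leading to permanent discontinuation, so such a stop may still be captured. What stands is a mismatch of wording.

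**Conclusion.** Two inconsistencies are wrong as written and should be fixed.

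- Section 2.8 item 3b does not score the rule that Appendix 1 applies. Two of its three items take a different form, one has no threshold value, and five of eight Appendix 1 triggers are not listed, with no statement on completeness. A required stop can therefore go unregistered in a 100% compliance outcome.
- The approval requirement in section 5.2 contradicts one of the five STOP events, event 1.

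The hypotension wording in 2.4 and 8.2.2 is secondary.

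The counts come directly from the text; the total of eight depends on splitting events 2 and 3 into their separate triggers. The 15 to 29 minute lags and the 2.2 average rest on assumed step changes in cardiac index and on a 2.0 limit for item 3b. They show that a stop can be missed, not how often it would be. Nothing here shows a patient left unprotected, since the treating clinician can have the infusion stopped for worsening shock. No efficacy estimate depends on the point. It matters because this single-arm study of up to 10 patients is meant to show that the protocols can be followed before a larger trial uses them.

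**What to change.** 1. **Section 2.8 item 3b.** Replace the list with all five Appendix 1 STOP events at their Appendix 1 thresholds, each scored yes or no for whether the infusion was stopped as directed. If 30-minute averages are intended, for example because cardiac index readings are noisy, write them into events 2 and 3, with values, so that one rule is both used and scored.
2. **Section 5.2.** Say that after a STOP event esmolol is restarted only as Appendix 1 states for that event. State in event 1 whether approval is needed.
3. **Sections 2.4 item 3b and 8.2.2.** Say that hypotension is handled by vasopressor titration, volume reassessment and the Appendix 1 STOP events. A stop based on MAP would be a clinical choice for the sponsor and is not part of this fix.

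The cost is a protocol wording amendment, with no added patients, procedures or staff. The downside is a few more events to score and a compliance figure that may look less favourable. If averages are moved into Appendix 1 instead, the bedside rule becomes slower to trigger, and the sponsor's clinicians should accept that explicitly.

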2.5 Inclusion criteria

1. Age \geq 18 years
2. Within 48 hours of admission to the ICU and septic shock (sepsis present at time of admission)
 - a. Septic shock defined by consensus criteria as
 - i. At least two SIRS criteria
 - ii. Suspected or documented infection
 - iii. Receiving vasopressors to treat hypotension after at least 20 ml/kg intravenous crystalloid volume expansion
3. Receiving vasopressors through a central venous catheter for more than 60 minutes.
4. Arterial catheter in place or expected to be placed imminently.
5. Heart rate $>$ 90/min while receiving vasopressors for more than 60 minutes.
6. Adequately volume expanded, as manifest by any of the following, performed as part of routine clinical care (i.e., no study procedures will be performed before signed consent). **If none of these measures are clinically available, the clinical attending must confirm that volume expansion is adequate.** (After enrollment, a final safety check will confirm the adequacy of volume expansion.)
 - a. Central venous pressure (CVP) $>$ 15 mm Hg.
 - b. Negative Passive-Leg Raise (PLR) maneuver ($<$ 10% increase in cardiac output after PLR).
 - c. No cardiac output response ($<$ 10% increase) after rapid infusion ($<$ 5 min) of 250 ml of IV crystalloid (i.e., a graded volume expansion challenge [GVEC]).
 - d. For patients who happen to be breathing passively on a positive pressure mechanical ventilator delivering at least 8 ml/kg tidal volumes and in normal sinus rhythm, stroke volume variability $<$ 10% (such patients are acknowledged to be uncommon; *the protocol does not recommend or require the induction of passive breathing*).

2.6 Exclusion criteria

1. Lack of informed consent.
2. Currently receiving ECMO.
3. Known pregnancy or nursing.
4. Patient is a prisoner.
5. Patient on hospice (or equivalent comfort care approach) at or before the time of enrollment.
6. Known or current atrial fibrillation.
7. Previously enrolled in the trial.
8. Known allergy to esmolol or vehicle (see Appendix 2 for BREVIBLOC vehicle ingredients).
9. Receipt of nodal blocking agents (see Appendix 3 for list of such agents) within three half lives
10. Hemoglobin $<$ 7 gm/dl.
11. Cardiac arrest within 24 hours.
12. Pulmonary hypertension (moderate or severe), from documented history of prior right heart catheterization or current evidence on TTE of **any** of the following
 - mPAP \geq 35mmHg

- SPAP \geq 60mmHg
13. Cardiovascular collapse, as manifested by inability to achieve a MAP of 65 mmHg with vasopressor therapy.
 14. Cardiogenic shock, as defined by **any** of the following
 - Cardiac index \leq 2 L/min/m²
 - Ejection fraction \leq 25%
 - ScvO₂ \leq 60%
 - Current infusion of any dose of dobutamine, milrinone, or dopamine
 - Current infusion of epinephrine for clinically diagnosed cardiogenic shock
 15. Significant atrioventricular dysfunction
 - Sick sinus syndrome
 - PR interval > 200 msec
 - Current evidence or prior history of Grade 2 or Grade 3 heart block
 - Pacemaker or plans to place a pacemaker
 16. Pheochromocytoma or status asthmaticus
 17. Receiving clonidine, guanfacine, or moxonidine
 18. Hemoglobin < 7 gm/dl
 19. Cardiovascular collapse (failure to achieve MAP of 65mmHg)
 20. Cardiac arrest within 24 hours
 21. Worse than moderate aortic stenosis
 - Known aortic stenosis, with any of (1) mean gradient \geq 40 mmHg OR (2) maximum gradient \geq 60mmHg OR (3) aortic valve area \leq 1.0cm² OR (4) aortic valve area index \leq 0.85cm²/m² body surface area.
 22. Worse than mild mitral stenosis
 - Known mitral stenosis, with any of (1) valve area \leq 1.5 cm² OR mean gradient \geq 5 mmHg.

2.7 Sample size: The study will enroll up to 10 patients at 1 center.

2.8 Non-clinical outcomes for ROLL-IN:

1. Proportion of eligible patients consented
2. Proportion of compliance with final safety check
 - a. Protocol compliance is considered adequate where compliance is 100% for the safety check.
3. Proportion of protocol compliance
 - a. For the esmolol titration protocol, each hour (the closest value of heart rate to the hour) during the esmolol infusion will be determined to be “in range” or “out of range,” with 3bpm margin for compliance (i.e., heart rate 77 to 93bpm). The initiation and cessation of esmolol will also be included as a timepoint for evaluation of compliance. Protocol compliance is considered adequate where overall compliance on hourly checks is >80%.
 - b. For STOP events, protocol compliance is considered adequate at 100%.
 - i. 30min moving average of cardiac index below threshold
 - ii. 30min moving average of norepinephrine infusion rate above threshold
 - iii. Clinician determines that shock has substantially worsened on esmolol.

- c. For VOLUME EXPANSION events, protocol compliance is considered adequate at 90%.
- 4. Amount of research coordinator time spent on different tasks

2.8.1 Anticipated primary clinical outcome for main trial (this will also be recorded for ROLLIN): Organ-failure-free days at 28 days. An organ-failure-free day is defined as a calendar day on which the patient receives none of (a) vasopressor therapy, (b) mechanical ventilation, or (c) renal replacement therapy.

2.8.2 Anticipated secondary clinical outcomes for main trial (these will also be recorded for ROLLIN):

1. All-cause hospital mortality
2. All-cause 28-day and 90-day mortality
 - a. Mortality will be ascertained through telephone followup for patients who were discharged alive before 90 days.
3. Peak serum high-sensitivity troponin
 - a. Troponin will be measured on day 0 and day 1.
4. LV global longitudinal strain at 24 hours
5. Time to transition to quiescent vascular phenotype, as defined by serum Angpt-2 level < 1ng/ml.
6. ICU-free days to day 28
 - a. Patients who die before 28 days will be assigned -1 ICU-free days, using a methodology similar to that used for organ-failure-free days.
7. Cardiogenic shock/requirement for inotropes through day 14. This is a binary variable and is met when any of the following is present
 - a. Dobutamine or milrinone infusion at any dose, lasting > 60min
 - b. $CI \leq 2$ L/min/m² lasting > 30 min on NICOM
 - c. $ScvO_2 \leq 60\%$ on any measurement
8. Development of second or third degree heart block.

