4.3.1 List of Exclusions and Reason for Exclusions

Exclusion Criterion	Justification/Description
Cardiogenic shock	Safety consideration: β -blockade may worsen preexisting cardiogenic shock. Cardiogenic shock defined as any one of 
 Cardiac Index ≤ 2 L/min/m² ScvO₂ $\leq 60\%$ Ejection Fraction $\leq 25\%$ Current infusion of any dose of dobutamine, milrinone, or dopamine Current infusion of epinephrine to treat clinically diagnosed cardiogenic shock.
Preexisting heart block	Safety consideration: β -blockade may worsen heart block. Defined as any of the following 
 Sick sinus syndrome PR interval > 200 msec Any current evidence or history of Grade 2 or Grade 3 heart block Pacemaker or plans to place a pacemaker
Atrial fibrillation at time of enrollment	Substantial noise associated with exposure, hemodynamic measurements, and outcomes; may require independent heart rate control or cardioversion.
Current nodal blockers or anti-arrhythmic agents	Safety consideration: risk of excess nodal blockade. Increased experimental noise. Receipt of any of the following within 3 half lives (see full list in Appendix) 
 Non-dihydropyridine calcium channel blockers Digitalis Anti-arrhythmics (e.g., amiodarone, dronedarone, mexiletine) Beta blockers
Receiving clonidine, guanfacine, or moxonidine	Safety issue
Moderate or severe pulmonary hypertension	Possible safety consideration; risk of hemodynamic deterioration. Defined as a documented history of prior right heart catheterization or current evidence on TTE of any of the following. 
 mPAP ≥ 35 mmHg SPAP ≥ 60 mmHg
Allergy to esmolol or vehicle	Rare, but required for patient safety.
Admitted for hospice or comfort care	Incomplete and biased data on both exposure and outcome.
Inability to obtain consent within 48 hours of ICU admission	This study does not qualify for waiver of consent
Active pregnancy or nursing	Physiology of pregnant patients distinct; potential risks to fetus unknown; drug levels in breast milk.
Prisoners	Septic shock is not specific to prisoners, so ethical concerns emphasize the protection of autonomy.
Previously enrolled in this trial	Violation of the independence assumption.
Pheochromocytoma or status asthmaticus	Safety issue associated with beta blockade

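### Appendix 1 has no rule for a nodal blocker ordered during the esmolol infusion, and its STOP 1 restart omits the approval that section 5.2 requires

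*Combined protocol and SAP*

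**What the plan says.** At entry, section 2.6 item 9 excludes "Receipt of nodal blocking agents (see Appendix 3 for list of such agents) within three half lives". The table in section 4.3.1 gives the reason as "Safety consideration: risk of excess nodal blockade", and adds experimental noise. Appendix 3 lists the agents.

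Once esmolol runs, Appendix 1 governs the dose by heart rate: "Increase by 20 mcg/kg/min every 20 minutes as long as HR > 90 bpm, to a maximum dose of 100 mcg/kg/min". It gives one hold, "Up-titrations should not occur during a REASSESS VOLUME STATUS event", and lets the clinician or investigator choose a smaller upward step. The rate comes down when heart rate falls below 80 bpm. Exposure has no fixed length: "Study drug infusion is completed 3 hours after vasopressor infusions have stopped".

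For a heart rate of 60 bpm or lower, STOP 1 says to "immediately stop infusion for 20 minutes, then restart at half the previous infusion rate, rounded to nearest 10 mcg/kg/min", with one further condition: "Do not resume infusion until HR > 70 bpm". STOP 2 and STOP 3 each state that a study physician must approve resumption. STOP 4 and STOP 5 do not allow resumption. Section 5.2 applies to STOP events generally and bars a restart unless an investigator explicitly approves it.

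**The concern.** The reason for the entry exclusion does not lapse when the infusion starts. If additive nodal blockade matters enough to keep a patient out, the titration protocol should say what happens when a second agent is ordered mid-infusion. It does not, so bedside staff following Appendix 1 have no instruction to pause upward steps or call the study physician.

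The restart after STOP 1 is where this matters most. A heart rate of 60 bpm or lower is a plausible first sign of combined blockade, yet the appendix sends staff back to esmolol on elapsed time and heart rate alone. Staff working from the appendix could restart without the approval that section 5.2 demands.

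The study exists to test whether these procedures are adequate (sections 2.2 and 3.3), and section 7.2 says its data will support rapid initiation of a much larger trial. A gap left here may be carried forward.

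**Working it through.** No arithmetic applies. The check is a reading of every place where a rule on nodal blockers after enrollment could stand.

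**1. Is there a rule on co-administration during the infusion?**

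- Sections 2.6 and 4.3.1: the exclusion applies at entry.
- Sections 2.4 and 5.1.1: the final safety check comes before the first dose of esmolol. Nothing says that it is repeated.
- Sections 5.2, 8.2 and 10: no restriction on Appendix 3 agents.
- Appendix 1 has five STOP events: heart rate of 60 bpm or lower; vasopressor escalation or clinician-judged worsening; cardiogenic shock; bronchospasm; grade 2 or 3 heart block. Giving an Appendix 3 agent triggers 0 of the 5.
- Appendix 1 has two triggers for reassessing volume status: low urine output and a vasopressor increase. Giving an Appendix 3 agent triggers 0 of the 2.
- Figures 1 and 2 were not available to me. Section 5.1.1 describes them as covering screening and the pre-infusion check, so an on-infusion rule there is unlikely.

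**2. Do the heart-rate rules make a co-medication rule unnecessary?**

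Upward steps need a heart rate above 90 bpm, so marked slowing is not present when a step is taken. But the entry rule works differently. Every candidate must have a heart rate above 90 bpm to qualify (section 2.5 item 5), and a recent nodal blocker still excludes that candidate. At entry, then, the protocol does not accept a rate above 90 bpm as sufficient reassurance. During the infusion, Appendix 1 allows the next upward step on that same rate, with no question about other drugs.

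**3. Do the restart rules agree?**

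| Event | Restart condition in Appendix 1 | Approval stated there? |
|---|---|---|
| STOP 1 | 20 minutes elapsed and heart rate above 70 bpm, at half rate | No |
| STOP 2, STOP 3 | Study-physician approval | Yes |
| STOP 4, STOP 5 | No resumption | Not applicable |

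Section 5.2 requires investigator approval for STOP events without exempting STOP 1. Read together, approval is needed, but the document used for titration leaves it out for STOP 1. Neither place says that the approval should include a review of other nodal blockers.

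**The case against.** The strongest reply is that the protocol controls by effect, whatever the cause. Esmolol comes down below 80 bpm, and faster at 70 bpm or lower. It stops at 60 bpm or lower, for cardiogenic shock, for clinician-judged worsening and for grade 2 or 3 block. Section 8.2 adds continuous cardiac-output monitoring and discontinuation for hypotension or excessive bradycardia. Section 8.1 notes that esmolol's effects reverse within minutes. The study has up to 10 patients at one center, with safety committee review at 3 and at 6 patients. All of this stands, and it is why the point is minor. It does not close the gap, because these safeguards respond after the combined effect has appeared, and quick reversal is claimed for esmolol, not for a second agent.

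A reader might infer that the dosing rules themselves bring about the combination. They do not: Appendix 1 doses esmolol only, and a clinician must order the second drug. In a single-arm study with no blinding described, that clinician can be expected to know that esmolol is running.

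A reader might also infer that resumption after surgery rests on cardiac index and volume status alone. Section 5.2 sets these as preconditions, explained by changes expected during surgery. It does not rule out other review, so naming a drug check there is optional.

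Finally, it can be said that the STOP 1 mismatch is editorial, since section 5.2 already requires approval. That is right about what the protocol as a whole requires. The two texts still give different restart instructions, and one sentence settles it.

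**Conclusion.** The point holds as a minor safety refinement with two parts. First, no rule covers an Appendix 3 agent given during the infusion, although section 4.3.1 treats recent use as a safety matter at entry. Second, STOP 1 directs a restart without the approval step that section 5.2 requires.

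The first part rests on reading the entry exclusion as applying at entry only, and on the unseen figures holding no contrary rule. The second rests on the text alone.

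The documents give no frequency for co-administration, so no event rate or expected harm is claimed. Three larger readings are tempting:

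- The speed with which the dose can reach its cap, or the size of a STOP 1 restart relative to a starting dose, might be taken to measure the hazard. These figures describe ordinary titration in any patient and do not depend on a second drug.
- The hourly heart-rate compliance result in section 2.8 item 3a might be thought materially distorted by a second drug or by new atrial fibrillation. The documents give no share of affected hours, so this cannot be shown.
- Section 4.3.1 might be read as declaring the combination unsafe. It names a risk as a safety consideration, and no more.

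**What to change.** Add one rule to Appendix 1: if an Appendix 3 agent other than study esmolol is given during the infusion, make no further upward step, and continue or restart the infusion only with the study physician's explicit approval. The exception is needed because Appendix 3 itself lists esmolol.

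Add one sentence to STOP 1 stating that restart needs the approval required by section 5.2, including a check for another nodal blocker. Optionally, name the same check in section 5.2 for resumption after surgery.

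The rule bans no treatment that the clinical team wants to give. It needs no table of half-lives, which the documents do not supply, because the decision rests with the study physician. The cost is two short insertions, or three with the optional one, and an occasional call. Affected patients may receive slightly less esmolol. Holding upward steps or waiting for approval may add a few out-of-range hours to the heart-rate compliance measure.
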